#### Adjustments to visit windows

Whenever possible and safe to do so, as determined by the investigator's discretion, participants should complete the usual SoA. To maximize the possibility that these visits can be conducted as on-site visits, the windows for visits may be adjusted, upon further guidance from the sponsor. This minimizes missing data and preserves the intended conduct of the study.

For participants whose visits have extended windows, additional study intervention may need to be provided to avoid interruption and maintain overall integrity of the study.

The primary endpoint visit and end of treatment visit, Visit 5 (Week 12), should be completed per original schedule whenever possible and safe to do so. The visit window should be within  $\pm 3$  days relative to the target visit date.

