4.1. General Considerations

Statistical analysis of this study will be the responsibility of Lilly or its designee.

Any change to the data analysis methods described in the protocol will require an amendment *only if* it changes a principal feature of the protocol. Any other change to the data analysis methods described in the protocol, and the justification for making the change, will be described in the statistical analysis plan or clinical study report. Additional exploratory analyses of the data will be conducted as deemed appropriate.

Nominal significance levels:

All tests of treatment effects will be conducted at a 2-sided alpha level of 0.05, unless otherwise stated, and all confidence intervals will be given at a 2-sided 95% level.

Timing of Primary Analysis:

Primary analysis will be performed at database release after Last Participant Last Visit (LPLV).

Definition of baseline:

Baseline is defined as the last non-missing measurement recorded on or before the date/time of first dose. If the measurement time is not specified, it is assumed that any measurement taken on the date of first dose occurred prior to dosing.

Populations for analysis:

- Analyses will use the EAS to evaluate the primary efficacy estimand for all (secondary and exploratory) endpoints.
- Safety analysis will be performed on the SS.

Pooling of data:

Study data will be pooled across centers.

Analysis Windows:

Visit windows will be defined for by-visit summary and analysis purposes. Summary data such as adverse events and concomitant medications which are not reported by visit will not use visit windows. Visit labels will be assigned to each post-baseline record based on the windows or intervals for study day relative to the date of first dose. A record with the study day closest to the target visit day (week \times 7 days + 1) will be chosen when multiple records fall in the same visit window. In case of a tie, the record with the earlier date will be chosen. If Day 1 is missing, the closest visit on or before the date of first dose will be used as baseline. All visits will be included in the summary tables for worst post-baseline values.

All efficacy and safety analyses will be based on the visit windows in Table 1.

Study Day Relative to First Dose	Visit	Target Day
Study day ≤ 1	Baseline	1
$2 \leq study \ day \leq 43$	Week 4 (Visit 3)	29
$44 \leq \text{study day} \leq 81$	Week 8 (Visit 4)	57
$82 \leq study \ day \leq 88$	Week 12 (Visit 5)	85

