- A treatment-emergent high result is defined as a change from a value less than or equal to the high limit at baseline to a value greater than the high limit at any time during the Treatment and Follow-up periods.
- A treatment-emergent low result is defined as a change from a value greater than or equal to the low limit at baseline to a value less than the low limit at any time during the Treatment and Follow-up periods.
 - Laboratory normal ranges will be provided by the Central Lab.

An MMRM using REML model will be used to analyze the changes in lipid panel parameters from baseline to all scheduled post-baseline visits. The model will include visits and baseline HbA1c category ($\leq 8.0\%$, >8.0%) as fixed effects and baseline value of the dependent variable as a covariate.

Vital signs:

Summary tables presenting observed values and changes from baseline will be presented for vital sign data, *systolic blood pressure (mmHg), diastolic blood pressure (mmHg), pulse rate (bpm),* weight (kg), Waist Circumference measurement (cm) and BMI for participants in the Safety set. For height (cm), only observed values will be summarized at baseline.

Height and weight measurements will be used to calculate BMI, with following formula:

 $BMI = weight (kg) / [height (m)]^2$

Descriptive summaries by nominal visit will be provided for baseline and postbaseline values as well as change from baseline values. If 2 records are taken at the same visit, they will be averaged prior to being used for data summaries and analyses.

An MMRM using REML model will be used to analyze the changes in vital signs from baseline to all scheduled post-baseline visits. The model will include visits and baseline HbA1c category ($\leq 8.0\%$, >8.0%) as fixed effects and baseline value of the dependent variable as a covariate.

Counts and percentages of patients with treatment-emergent abnormal sitting systolic blood pressure (BP), sitting diastolic BP, and pulse will be presented. The criteria for identifying patients with treatment-emergent vital sign abnormalities are stated in Table 4.

Table 4.Categorical Criteria for Abnormal Treatment-Emergent Blood Pressure and
Pulse Measurement

Parameter	Low	High
Systolic BP (mm Hg) (Supine or sitting – forearm at heart level)	Observed value ≤ 90 and decrease from baseline ≥ 20	Observed value ≥ 140 and increase from baseline ≥ 20

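### SAP Table 1 ends at Day 88, so a scheduled Visit 5 held four or more days late gets no Week 12 label and its HbA1c, weight and FSG are left out of the Week 12 analyses

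*SAP*

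**What the plan says.** SAP 4.1 (Analysis Windows) sets the labelling rule: "Visit labels will be assigned to each post-baseline record based on the windows or intervals for study day", counted from first dose. It then applies the rule to everything: "All efficacy and safety analyses will be based on the visit windows in Table 1". Table 1 has three post-baseline rows:

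- Week 4: Days 2 to 43, target Day 29
- Week 8: Days 44 to 81, target Day 57
- Week 12: Days 82 to 88, target Day 85

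The nearest-to-target rule chooses only among records already in the same window. The one stated exception is that summaries of worst post-baseline values use all visits.

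SAP 4.3.2 takes the primary estimate from the Week 12 LS mean of the MMRM, without imputation and under missing at random. SAP 4.4.2 applies the same approach to weight and FSG.

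The Schedule of Activities (Protocol 1.3) allows ±3 days at each of Visits 3, 4 and 5. For exceptional circumstances, Protocol Appendix 8 says that "the windows for visits may be adjusted, upon further guidance from the sponsor", but it still asks for Visit 5 within ±3 days.

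For vital signs, a group that includes weight, SAP 4.6.4.1 says: "Descriptive summaries by nominal visit will be provided for baseline and postbaseline values as well as change from baseline values".

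**The concern.** A rule meant to tidy visit timing removes observed values of the primary endpoint. The EAS definition (SAP 3) has two exclusions: participants enrolled inadvertently, and data after permanent discontinuation or prohibited medication. Lateness is neither, so Table 1 in effect adds a third exclusion without saying so. Protocol 9.3.2 and SAP 4.3.2 both model the change at each scheduled post-baseline visit, and SAP 4.9 declares no departure from the protocol's analyses. A late Visit 5 is still a scheduled visit.

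Three things are at stake: some precision at the one time point that carries the hypothesis test, needless reliance on the missing-data assumption where a measurement exists, and ambiguity for the programmer about which labelling rule applies.

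**Working it through.** **Plan's own figure.** The inputs are in Protocol 9.5 and SAP 5: n = 150, mean change 0.3, variability 1.1 (taken here as the SD of the change), one-sample t-test, two-sided 0.05.

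- Noncentrality = (0.3 / 1.1) × √150 = 3.34.
- Power from the noncentral t with 149 df = 91.3%. The normal check is Φ(3.34 − 1.96) = 91.6%.
- The stated figure of at least 90% is reproduced. The smallest n with 90% power is 144, so the margin is 6 participants.

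**Window arithmetic.** The target day is week × 7 + 1, which gives 12 × 7 + 1 = Day 85.

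| Visit | Protocol tolerance | Table 1 row | Width in days | Days allowed before / after target |
|---|---|---|---|---|
| Week 4 | ±3 | 2–43 | 43 − 2 + 1 = 42 | 27 / 14 |
| Week 8 | ±3 | 44–81 | 81 − 44 + 1 = 38 | 13 / 24 |
| Week 12 | ±3 | 82–88 | 88 − 82 + 1 = 7 | 3 / 3 |

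A Week 12 visit 3 days late is on Day 88 and is labelled. One 4 days late is on Day 89 and has no label, nor has any later one. A Week 8 visit 24 days late keeps its label.

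**What is lost.** HbA1c and weight are scheduled at every visit, so a participant with a Week 4 or Week 8 value stays in those models and only the Week 12 value is missing. FSG comes from clinical chemistry, which the Schedule of Activities places after baseline only at Visit 5 and early discontinuation. A late FSG therefore has no scheduled earlier post-baseline value to draw on. Protocol 1.3 also has a non-fasting sample repeated on another day without a deviation. If Visit 5 is on Day 88, the fasting repeat falls on Day 89 or later and is unlabelled.

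**Size.** The share of late visits is not in the documents, so the shares below are assumptions. Power is for a complete-case t-test on the plan's inputs.

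| Assumed share of Week 12 values lost | n | Power |
|---|---|---|
| 0% | 150 | 91.3% |
| 2% | 147 | 90.7% |
| 4% | 144 | 90.2% |
| 5% | 142 | 89.8% |
| 10% | 135 | 88.2% |
| 20% | 120 | 84.2% |

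These overstate the loss for HbA1c, because the MMRM uses the Week 4 and Week 8 values.

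**The case against.** The strongest defence is that Days 82 to 88 are exactly the protocol's tolerance for Visit 5, and that Appendix 8 aims to hold that visit to ±3 days even in exceptional circumstances. So only out-of-tolerance visits are affected. That stands, and it limits the number. It does not show a deliberate policy: Visits 3 and 4 carry the same tolerance and Table 1 does not enforce it there, and no reason is given for treating Week 12 differently.

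A second defence concerns exposure. With weekly dosing from Day 1, the twelfth dose falls on Day 1 + 11 × 7 = Day 78, so Day 89 is 11 days after it. Protocol 8.1.2 says that no further study drug is given at Visit 5. Late values may thus be partly off drug, which matters for an estimand that assumes continued treatment. This is not certain: the documents do not give the number of pens dispensed, doses may slip, and Appendix 8 foresees extra supply when windows are extended. It supports a stated upper limit. It does not support a silent cut-off at Day 88, which is already 10 days after Day 78.

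Third, SAP 1.2 describes the treatment period as 12 weeks, so a late visit might be thought outside it. SAP 1.2 also defines the period as running from Visit 2 to Visit 5. A strict 84-day count would exclude Days 86 to 88, which Table 1 keeps.

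A reader might infer more than the documents support:

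- **That the participant leaves the primary analysis.** Only the Week 12 record does, if an earlier HbA1c exists.
- **That CGM endpoints are lost too.** They come from a 14-day session before the visit, and the SAP does not say which date labels a session.
- **That the windows alone would make the two weight analyses disagree.** The vital-sign tables use the Safety Set and the endpoint uses the EAS, so they can differ anyway.
- **That the estimate is biased.** Administrative lateness may well be missing at random, and nothing in the documents shows otherwise.

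**Conclusion.** The gap is real and follows from the text: as written, a scheduled Visit 5 on Day 89 or later contributes no HbA1c, weight or FSG to the Week 12 estimates, while late visits at Weeks 4 and 8 are kept. The probable cost is small, about 1.5 power points at an assumed 5% loss and about 3 at 10% on a complete-case basis, and less for HbA1c under the MMRM. On that calculation, losing more than 6 of 150 Week 12 values takes power below 90%, and the sample-size statements show no allowance for dropout. The figures rest on reading 1.1 as the SD of the change and on late-visit rates that the documents do not supply. The case for a change is that observed primary-endpoint data should not become missing through an unexplained edge in a table, and that the repair is cheap.

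**What to change.** In SAP 4.1, do one of the following:

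1. Label the scheduled Visit 5 by its nominal (CRF) visit, and use study-day windows only for early-discontinuation and unscheduled records.
2. Extend the Week 12 row beyond Day 88 for EAS records, with a prespecified upper limit tied to time since the last dose. An open-ended row would admit values taken long after dosing stopped.

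In either case, report how many Visit 5 samples fall outside Days 82 to 88, and add a sensitivity analysis restricted to samples within Days 82 to 88. Reconcile the reference to nominal visits in SAP 4.6.4.1 with the statement that Table 1 governs all analyses.

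The cost is a sentence or a table row in the SAP and minor programming. The downside is a slightly wider spread of Week 12 timing, with some values taken longer after the last weekly dose. The sensitivity analysis would show whether that matters.

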### 9.3.5.3. Central Laboratory Measures and Vital Signs

Values and changes from baseline to postbaseline values of appropriate central laboratory measures and vital signs will be summarized at each scheduled visit.

The analysis model to make comparisons within treatment relative to continuous change from baseline values assessed over time will be an MMRM, with terms: visit, country, and baseline measurement as covariates.

An unstructured covariance structure will model relationship of within-participant errors.

The percentages of participants with treatment-emergent abnormal, high, or low laboratory measures at any time will be summarized.

A treatment-emergent abnormal value is defined as a change from normal value at baseline to an abnormal value at any time during the follow-up.

A treatment-emergent high result is defined as a change from a value less than or equal to the high limit at baseline to a value greater than the high limit at any time during the Treatment and Follow-Up periods.

A treatment-emergent low result is defined as a change from a value greater than or equal to the low limit at baseline to a value less than the low limit at any time during the Treatment and Follow-Up periods.

High and low limits will be provided in SAP.

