2.1. Multiplicity Adjustment

Multiplicity adjustment will not be implemented in this study.

3. Analysis Sets

For the purposes of analysis, the following analysis sets are defined:

Population/Analysis Set	Description
Screened population	All participants who signed informed consent
Modified intent-to-treat population (mITT)	• All participants who are exposed to at least 1 dose of study intervention
Efficacy Analysis Set (EAS)	• This analysis set will be used to estimate the efficacy estimand for the primary objective, and for all other (secondary, exploratory) endpoints.
	• Data obtained during the treatment period from the mITT population, excluding (1) participants who were inadvertently enrolled* and (2) data after permanent discontinuation of treatment or initiation of prohibited medication.
Safety Analysis Set (SS)	• This analysis will be used to assess the safety of study treatment
	• Data obtained during the Treatment Period from the mITT population, regardless of adherence to treatment or initiation of prohibited medication.

* An inadvertent enroller refers to a subject who does not meet inclusion/exclusion criteria but receives study intervention.

4. Statistical Analyses

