When count data are presented, the percentage will be suppressed when the count is zero in order to draw attention to the non-zero counts. A row denoted "Missing" will be included in count tabulations where specified on the shells to account for dropouts and missing values. The denominator for all percentages will be the number of subjects in that treatment within the analysis set of interest, unless otherwise specified.

The analysis model to make comparisons within treatment relative to continuous measurements assessed over time will be an MMRM with terms for:

- Visits, as fixed effects
- Baseline HbA1c ($\leq 8.0\%$, > 8.0%), as a covariate
- Baseline measurement, as a covariate

For analyses of HbA1c, continuous baseline HbA1c will be included in the model instead of baseline HbA1c category. An unstructured covariance structure will model the relationship of within-participant errors.

Logistic regression may be used to examine the within-treatment effect from baseline at 12 weeks in binary efficacy outcomes. The negative binomial regression model will be used to measure the within-treatment effect of discrete count measures if deemed appropriate.

Summary of intercurrent events:

The number of participants who experience an intercurrent event will be summarized in a table by event type (treatment discontinuation for any reason, or initiation of prohibited medication) and visit. For each visit, the number of intercurrent events which happened before or during the measurements taken on that visit will be calculated, excluding the events which happened during or before the measurements taken at the previous visits.

Furthermore, the number of participants without any intercurrent events will be presented by visit too. At each visit the number and percentage of participants without intercurrent events will be shown.

All analyses will be conducted using SAS Version 9.4 or higher.

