- Hepatic Hematology Panel: Hemoglobin, Hematocrit, Erythrocytes (RBCs - red blood cells), Leukocytes (WBCs white blood cells), Differential (Neutrophils, segmented Lymphocytes, Monocytes, Basophils, Eosinophils, Platelets, Cell morphology (RBC and WBC).
- Hepatic Clinical Chemistry Panel: Total bilirubin, Direct bilirubin, Alkaline phosphatase (ALP), Alanine aminotransferase (ALT), Aspartate aminotransferase (AST), Gamma-glutamyl transferase (GGT), Creatine kinase (CK)
- Hepatic Coagulation Panel: Prothrombin time, INR (PT-INR)
- Urine Chemistry: Drug screen
- Haptoglobin
- Hepatitis A virus (HAV) testing: HAV total antibody, HAV IgM antibody
- Hepatitis B virus (HBV) testing: Hepatitis B surface antigen (HBsAg), Hepatitis B surface antibody (anti-HBs), Hepatitis B core total antibody (anti-HBc), Hepatitis B core IgM antibody, HBV DNA
- Hepatitis C virus (HCV) testing: HCV antibody, HCV RNA
- Hepatitis D virus (HDV) testing: HDV antibody

- Hepatitis E virus (HEV) testing: HEV IgG antibody, HEV IgM antibody, HEV RNA
- Anti-nuclear antibody (ANA)
- Anti-smooth muscle antibody (ASMA)
- Anti-actin antibody
- Epstein-Barr virus (EBV) testing: EBV antibody

Laboratory assessments will be performed by a central laboratory. All summaries will be based on the units provided by the central laboratory, no conversion will be done.

All relevant clinical laboratory tests will be classified as treatment emergent Low, Normal, and High, or Normal/Abnormal according to the normal ranges. This categorical data will be summarized in shift tables comparing the results at each scheduled post-baseline visit with those at the baseline visit. The percentages of participants with treatment-emergent abnormal, high, or low laboratory measures at each post-baseline visit will be summarized.

When there are multiple values within a visit for a particular laboratory variable, the worst value will be taken (worst being the smallest value for criteria below a certain threshold or the largest value for criteria above a certain threshold). If a participant has a value below the threshold and above the threshold, the value furthest from the threshold will be chosen.

A treatment-emergent abnormal value is defined as a change from normal value at baseline to an abnormal value at any time during the follow-up.

Definition of treatment emergent Low/High results:

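### The default denominator in SAP 4.1 keeps participants who cannot have, or cannot be seen to have, a treatment-emergent laboratory abnormality, so the reported laboratory percentages run low

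*SAP*

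**What the plan says.** SAP 4.1 (General statistical methods) gives the default: "The denominator for all percentages will be the number of subjects in that treatment within the analysis set of interest, unless otherwise specified".

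The laboratory summaries use the Safety Analysis Set. SAP Section 3 describes that set as "Data obtained during the Treatment Period from the mITT population, regardless of adherence to treatment or initiation of prohibited medication", and the mITT population as "All participants who are exposed to at least 1 dose of study intervention". Membership needs one dose; it needs neither a baseline nor a post-baseline measurement.

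SAP 4.6.4.1 then plans: "The percentages of participants with treatment-emergent abnormal, high, or low laboratory measures at each post-baseline visit will be summarized". It states no denominator for these percentages. Its definitions all carry a baseline condition. For normal/abnormal tests: "A treatment-emergent abnormal value is defined as a change from normal value at baseline to an abnormal value at any time during the follow-up". For a high result: "change from a value less than or equal to the high limit at baseline to a value greater than the high limit". The definition of a low result mirrors this.

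Protocol 9.3.5.3 describes the same summary over a different period: "The percentages of participants with treatment-emergent abnormal, high, or low laboratory measures at any time will be summarized". It gives no denominator either. SAP 4.9 declares no changes to the protocol-planned analyses.

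**The concern.** A treatment-emergent event has a built-in risk set: people who start on the right side of the limit and are measured again. The default denominator adds two groups that can contribute nothing to the numerator. These are participants already beyond the limit at baseline, and participants with no later sample. The percentage then mixes the rate of new abnormalities with the baseline prevalence of old ones and with missing data.

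The study has one arm, so there is no comparator in which the dilution could cancel. The absolute percentage is the safety result. The effect is largest for analytes often abnormal at entry. The eligibility rules in the protocol admit such participants: HbA1c must be 6.5% to 9.0%, which bears on glucose, and ALT may be as high as 3.0 times the upper limit of normal.

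**Working it through.** **The plan's own figure.** The plan gives no figure for this point. Its only derived figure is the sample size: 150 participants, a difference of 0.3 and an SD of 1.1 (taken as the SD of the change), for at least 90% power. The noncentrality is 0.3 / (1.1/√150) = 3.340, and a two-sided one-sample t-test at 0.05 has power 91.3%, which agrees. Nothing below depends on it; 150 serves only as an illustrative Safety Set size.

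**Does the default apply?** SAP 4.1 yields only where another denominator is specified. SAP 6.2 does specify a restricted one for compliance (participants dosed in the period concerned). SAP 4.6.4.1 specifies none for treatment-emergent laboratory values. On the supplied text, the default applies.

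**Size of the dilution.** For a given analyte and direction, let

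- N = participants in the Safety Set;
- b = share excluded from the event by their baseline value;
- m = share of the remainder with no evaluable post-baseline value;
- p = incidence among those at risk and measured.

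The number at risk and measured is N(1-b)(1-m), and expected events are pN(1-b)(1-m). Dividing by N as SAP 4.1 directs:

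reported percentage = p × (1-b)(1-m).

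The factor cannot exceed 1, so the direction is fixed. The documents give neither b nor m; the values below are assumptions.

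| b | m = 0 | m = 5% | m = 10% |
|---|---|---|---|
| 5% | 0.95 | 0.90 | 0.86 |
| 10% | 0.90 | 0.86 | 0.81 |
| 20% | 0.80 | 0.76 | 0.72 |
| 50% | 0.50 | 0.48 | 0.45 |

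Worked case: N = 150, b = 20%, m = 10%, p = 10%. At risk: 150 × 0.8 × 0.9 = 108. Expected events: 10.8. Reported: 10.8/150 = 7.2% instead of 10%.

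The other way round, 9 events print as 9/150 = 6.0%. They are 6.7% of 135 at risk, 7.5% of 120, or 12.0% of 75.

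**Vital signs.** SAP Table 4 works differently. Each criterion is a threshold plus a change from baseline, with no requirement that baseline be normal. Systolic pressure of 150 at baseline and 172 later meets the high criterion (at least 140, and a rise of 22 against the required 20). So b = 0 and the factor is 1-m: 0.95 to 0.90 for an assumed m of 5% to 10%. Vital signs are scheduled at every visit and at early discontinuation, so m should be small.

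**Period.** The SAP tabulates by visit; the protocol reports over any time. In the Schedule of Activities, chemistry and lipids have only Visit 5 or the early-discontinuation (ED) visit after baseline. For most participants the two versions coincide. They part for ED samples, which SAP Table 1 assigns to the Week 4 or Week 8 window if taken before Day 82; for unscheduled repeats; and for samples after Day 88, which fall in no window. In the Week 4 and Week 8 windows few participants have a chemistry sample, yet the default divides by everyone. One new high among three ED samples (an invented example) would print as 1/150 = 0.7%.

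**The case against.** The strongest reply is that the laboratory problem is already largely visible. SAP 4.6.4.1 plans shift tables against baseline, and SAP 4.6.4.6 adds shift tables by baseline category for ALT, AST, bilirubin and alkaline phosphatase. A reader can recover much of the at-risk denominator from these. Lipids also have a repeated-measures model, and fasting glucose is a secondary endpoint. The percentage of all treated participants is an interpretable quantity, though not the incidence among those at risk. With one arm, no between-group comparison is distorted. The table specifications are a separate document, not supplied, and may set another denominator. All of this stands as mitigation. It does not correct the headline percentage, and the governing SAP text should carry the rule.

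A reader might also infer more than the documents support:

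- **That vital-sign percentages are diluted by abnormal baselines.** Table 4 has no normal-baseline condition; only missing values act there.
- **That the exploratory CGM in-range composite is biased downward at Week 12.** SAP 4.1 allows a row for missing values where the shells specify it, and those shells are not available. Baseline sessions can be missing too, under the same 70% threshold, and no missing share is given for either time point. A bias is not demonstrated.
- **That no overall laboratory incidence can come out of the SAP.** Its definitions keep the any-time wording, SAP 4.1 brings all visits into worst post-baseline tables, and routine chemistry and lipids have one scheduled post-baseline time point. The mismatch with the protocol is real and undeclared, but small.
- **That safety incidences will be understated by some particular amount.** Eligibility up to 3.0 times the upper limit for ALT shows that abnormal baselines can occur, not how often.

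**Conclusion.** The point holds for treatment-emergent laboratory percentages. Followed as written, the SAP divides by participants whom its own definitions bar from having the event and by participants who were not measured again. The result equals the at-risk percentage times (1-b)(1-m). The direction follows from the text. The size does not: the range of 0.95 to 0.45 rests on assumed b of 5% to 50% and m of 0 to 10%, and it will differ by analyte and direction. The conclusion also assumes that the unseen table specifications do not already override the default.

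For vital signs the effect is small and comes only from missing values. The primary and secondary efficacy analyses and the sample size are unaffected. This is worth correcting because the percentages are absolute safety results and the correction is cheap.

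**What to change.** In SAP 4.6.4.1:

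- Set the laboratory denominator to Safety Set participants whose baseline value is not already abnormal in that direction (normal, for tests read as normal/abnormal) and who have at least one post-baseline value. For by-visit tables, require a value at that visit.
- Report the incidence at any time after baseline, including early-discontinuation and unscheduled samples, as Protocol 9.3.5.3 states. If by-visit percentages are kept as well, list them as an addition in SAP 4.9.
- For Table 4 vital signs, use participants with a baseline and at least one post-baseline value.
- Show the denominator beside each percentage, and carry the same rules into the table specifications.

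The cost is a few lines of SAP text and one denominator flag per analyte and direction. No new data are needed.
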